13.2 Safety Review

Both the risks listed in Section 4.1 and unknown risks will be monitored as follows: the participants will be given written and verbal instruction during the consenting process and at each telephone/zoom call will be asked if they have experienced any adverse effects. The subject will also have the opportunity to contact the study personnel or PI if they experience any adverse effects or significant discomfort from coolness among others.

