6.1 Risks

Version number 1.8 and January 23, 2024

The most common risks of the wrist cooling device in this study include a reaction that impairs blood flow to the hand and could make it worse for disorders such as Raynaud's phenomenal which is why people with Raynaud's and similar conditions should not take the part in the study. The participant may also experience the coolness as being uncomfortable.

To minimize the risk of adverse events, we will exclude subjects with any history of cold sensitivity to the wrist or hand. In addition, the participant may find the attachment of the device around the wrist to be uncomfortable. We will exclude subjects with a history of experiencing discomfort when placing anything such as a wristwatch on their wrist.

To mitigate discomfort for the device that when activated results in white plate cooling the skin underneath it to a temperature of 47°F we will instruct the participant to press the square button and the temperature will almost immediately increase to 60°F. If it is still uncomfortable the participant has the option of pressing the button again to further increase the temperature to 77°F. They have the other option to shut it off by holding the button down for 2 seconds. The device can also be removed immediately from the wrist which is attached by a Velcro connection that can be easily opened. To mitigate any discomfort for the device that when activated turns on the cooling fan only they will be instructed to press the square button for 2 seconds which will set off the device or they can immediately remove the device from their wrist.

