13.1 Definitions for Safety Assessment

The following definitions will be used in the assessment of safety:

Adverse Event (AE) is any untoward or unfavorable medical occurrence in a human subject, including any abnormal sign (for example, abnormal physical exam or laboratory finding), symptom, or disease, temporally associated with the subject's participation in the research, whether or not considered related to the subject's participation in the research.

Serious Adverse Event (SAE) is any adverse event that

- (1) results in death;
- (2) is life-threatening;
- (3) results in inpatient hospitalization or prolongation of existing hospitalization;
- (4) results in a persistent or significant disability/incapacity;
- (5) results in a congenital anomaly/birth defect; or
- (6) based upon appropriate medical judgment, may jeopardize the subject's health and may require medical or surgical intervention to prevent one of the other outcomes listed in this definition (examples of such events include allergic bronchospasm requiring intensive treatment in the emergency room or at home, blood dyscrasias or convulsions that do not result in inpatient hospitalization, or the development of drug dependency or drug abuse).

Life-threatening means that the event places the subject at immediate risk of death from the event as it occurred.

Version number 1.8 and January 23, 2024

Unanticipated Problem is defined as an event, experience or outcome that meets **all three** of the following criteria:

- is unexpected; AND
- is related or possibly related to participation in the research; AND
- suggests that the research places subjects or others at a greater risk of harm (including physical, psychological, economic, or social harm) than was previously known or recognized.

Possibly related means there is a reasonable possibility that the incident, experience, or outcome may have been caused by the procedures involved in the research

Unexpected means the nature, severity, or frequency of the event is not consistent with either:

- the known or foreseeable risk of adverse events associated with the procedures involved in the
 research that are described in (a) the protocol–related documents, such as the IRB-approved
 research protocol, any applicable investigator brochure, and the current IRB-approved informed
 consent document, and (b) other relevant sources of information, such as product labeling and
 package inserts; or

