- the expected natural progression of any underlying disease, disorder, or condition of the subject(s)
 experiencing the adverse event and the subject's predisposing risk factor profile for the adverse
 event.

Unanticipated adverse device effect means any serious adverse effect on health or safety or any lifethreatening problem or death caused by, or associated with, a device, if that effect, problem, or death was not previously identified in nature, severity, or degree of incidence in the investigational plan or application (including a supplementary plan or application), or any other unanticipated serious problem associated with a device that relates to the rights, safety, or welfare of subjects.

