13.3 Reporting Plans

Version number 1.8 and January 23, 2024

The Principal Investigator at BMC/BU Medical Campus will report Unanticipated Problems, safety monitors' reports, and Adverse Events to the BMC/BU Medical Center IRB in accordance with IRB policies:

- Unanticipated Problems will be reported to the BMC/BU Medical Campus IRB within 7 days of the investigator learning of the event.
- Adverse Events (including Serious Adverse Events) will be reported in summary at the time of
 continuing review, along with a statement that the pattern of adverse events, in total, does not
 suggest that the research places subjects or others at a greater risk of harm than was previously
 known.

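### Section 13.2 asks participants about adverse effects, an undefined term that may under-capture the adverse events that 13.1 defines regardless of cause and 13.3 reports in total

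*Combined protocol and SAP*

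**What the plan says.** Three parts of Section 13 have to work together.

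- **Definition (13.1).** The section opens "The following definitions will be used in the assessment of safety". An adverse event is any untoward medical occurrence associated in time with participation, "whether or not considered related to the subject's participation in the research". Serious adverse events are a subset, so a hospital stay counts whatever its cause.
- **Collection (13.2).** Participants receive written and verbal instruction at consent, and "at each telephone/zoom call will be asked if they have experienced any adverse effects". They may also contact the study team "if they experience any adverse effects or significant discomfort from coolness among others". The stated scope is broad: "Both the risks listed in Section 4.1 and unknown risks will be monitored as follows".
- **Reporting (13.3).** Adverse events, serious ones included, are summarised at continuing review, with a statement that "the pattern of adverse events, in total, does not" suggest greater risk than previously known.

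Section 6.1 names the foreseeable risks: "a reaction that impairs blood flow to the hand", discomfort from the coolness, and discomfort from the attachment around the wrist.

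**The concern.** The collection step uses a different term from the definition before it and the report after it. *Adverse effect* standing alone is defined nowhere. In ordinary speech an effect has a cause, and a participant in a device trial who is asked about adverse effects may well think only of what the device did. A chest infection, a fall or a hospital admission during the device weeks is an adverse event under 13.1, but a participant who sees no link to the device may not mention it.

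Two things depend on this. The statement on adverse events in total can be no more complete than the answers behind it. And relatedness, which is one of the three criteria for an Unanticipated Problem in 13.1, could in practice be screened by the participant before the investigator hears of the event. The blood-flow risk in 6.1 is a case in point: a participant may notice a change in the hand without recognising it as an effect of the device, and 13.2 states no specific prompt for it.

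**Working it through.** The point is about wording, and the plan gives no figure to reproduce. The check sets the sections side by side and then looks for any other safety question.

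**1. Terms**

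- 13.1: adverse event, relatedness not required, defined.
- 13.2, calls: adverse effects, not defined.
- 13.2, participant-initiated contact: adverse effects, or significant discomfort from coolness, with an open-ended close.
- 13.3: adverse events, in total.

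The term changes between definition and collection, then changes back for reporting.

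**2. How the document uses *adverse effect* elsewhere**

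The definition of an unanticipated adverse device effect in 13.1 covers "any serious adverse effect on health or safety or any lifethreatening problem or death caused by, or associated with, a device". The device link is added by the closing words. The protocol therefore does not treat *adverse effect* as device-related in itself, and the broad reading is available. But that reading depends on text that participants on a call do not have in front of them.

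**3. Other places where adverse events might be solicited**

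- Diaries (Sections 2 and 12): hot flash severity, and in weeks 3 to 6 whether the device was used. No adverse event entry is described.
- Final visit (Section 12 and the Appendix): questions about use of the devices. Section 16 adds a question on believed assignment. No adverse event question is stated.
- Schedule of events (Appendix): no adverse event row.

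The call question is the only solicitation stated.

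**4. How often it is asked**

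Section 12 plans 3 calls: 1 to 3 days before the first device starts, 1 to 3 days before the second starts, and in week 6 before the study ends. More calls are possible if the start is delayed. The first planned call precedes any device use, which leaves 3 − 1 = 2 planned calls after exposure begins. With so few occasions, the wording of the question carries most of the active safety collection.

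**5. Size**

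The documents give neither an expected event rate nor a proportion of events that this question would elicit. No estimate of under-capture can be derived from them.

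**The case against.** The strongest reply is that the broad reading is the intended one. The question covers any adverse effects and sets no device limit. Section 13.2 says unknown risks are monitored too. Section 13.1 says its definitions govern the safety assessment. The first call comes before any device is used, so a question put at that call cannot mean only effects blamed on a device. Participants also receive instruction at consent, and neither that material nor a call script is in the documents; it may already ask for all events and describe the hand symptoms to report.

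Most of this stands, and it rules out several stronger readings that a reader might infer:

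- *Events not blamed on the device are never solicited.* The text does not say so, for the reasons just given.
- *Spontaneous reports must reach a significance threshold.* In "if they experience any adverse effects or significant discomfort from coolness among others", the word *significant* qualifies only discomfort from coolness. Adverse effects carry no threshold, and the list is left open.
- *The comparison of events between devices is biased.* Only one device cools the skin, so attribution could plausibly differ by device. But no comparison of adverse events between devices is planned: the outcomes in Section 4.2 are hot flash severity and device use, and 13.3 calls for a summary.

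The reply does not remove the ambiguity. The stated scope and the definitions guide the study team, whereas the participant answers the question as heard. If unseen material resolves the matter, 13.2 can say so at no cost.

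**Conclusion.** The mismatch of terms is real and worth correcting. The one stated safety question uses an undefined term that can be heard as causal, while the definition and the report both cover events regardless of cause. The wording may under-capture events that participants consider unrelated, serious ones among them; it does not exclude them.

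This rests on two assumptions: that some participants or callers will take *adverse effects* in its causal sense, and that the consent instruction and any call script, which are not available here, do not already settle the meaning. The size of any loss is unknown. This is a modest improvement to safety capture; it does not touch the efficacy analysis.

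**What to change.** In 13.2, replace *adverse effects* with the defined term *adverse event* in both the call question and the participant-initiated route, and state the question to be used at the existing calls. For example: *Since we last spoke, have you had any new or worse symptom, illness, injury or medical visit, whether or not you think it is due to the device?*

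Follow it with short prompts for the three risks named in 6.1 (change in blood flow to the hand, discomfort from coolness, wrist discomfort from the attachment), worded identically in both device periods. Record the onset date and the device period (first or second, so that the blind is kept). State that the investigator, not the participant, judges relatedness under 13.1.

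The same edit can correct the cross-reference in 13.2: it points to Section 4.1 for the risks, but 4.1 is the study objective and the risks are in 6.1.

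The cost is a revision of 13.2 and of the wording used on calls, plus a few more minor, unrelated events to log. No visit, procedure or participant is added.

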9.1.2 Retention Procedures

The subject will be contacted by study personnel via telephone or zoom call 1-3 days before the expected date he/she will use the device during weeks 3 and 4 of the study and then a telephone or zoom call 1-3 days before the expected date when the participant will use the other randomly assigned device during weeks 5 and 6. The subject will be contacted during week 6 of the study before the study end date to remind them to come back and return the diaries and devices at their scheduled visit that was provided to them during their first visit. Those subjects who are participating in the study virtually will be contacted during week 6 of the study before the study end date to remind them to return the diaries and devices by FEDEX, UPS or USPS.

10 Screening Procedures

Once subjects have responded to the study flyer, ClinicalTrial.gov or word of mouth, they will be screened over the phone or by zoom to determine eligibility using brief screening agreement and pre-screening questionnaire. During the preliminary screening call, the subject will be asked about their medical history and inclusion/exclusion criteria. Completion of the preliminary anonymous screening for the potentially eligible participants will be documented in the study binder. The information to be retained in the study binder include study ID and answers to the pre-screening questionnaire. For the individuals with screening failure, no information will be retained. Once the subjects are determined to be eligible, they will be scheduled for their first visit to our clinical research space in the Vitamin D, Skin, and Bone Research Laboratory, located at [name] (BUSM), locally or virtually. The PI will consent the subjects either in person or virtually by zoom.

The eligibility data will be stored in [name] offices under lock and key. The door to [name]'s lab is accessed by those who have ID access to the lab. Electronic information will be stored on a departmental

Version number 1.8 and January 23, 2024

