The participant will be instructed that for the first 2 weeks that he/she will document in the diary labeled as Hot Flash diary each hot flash rating it as severe, moderate, or minimal without using the device. Study personnel will contact the participant by phone or zoom call 1-3 days before the expected date to start using the device that they were randomly assigned to use. During this call, they will be instructed at the beginning of week 3 to open up one of the two boxes (depending on which arm they are randomized into) that they were given during the first visit and begin using it. The device will be in the box with labeled instructions. They will be instructed that they can wear the device 24/7 i.e. all the time or they can place it on their wrist when they begin to experiencing a hot flash. The study personnel will also explain that during weeks 3 and 4 they will now be using the diary labeled as Hot Flash and Device Use. The study personnel will go over how to use this diary and how to record the severity of their hot flash and document whether or not they used the device.

If you are not available to use the device at the beginning of week 3, you will be allowed to keep documenting the severity of the hot flashes without using the device for another 2 weeks +3 days. You will be contacted by phone or zoom call again 1-3 days prior to the date you expect to start using the device.

At the end of week 4, they will be contacted again by the study personnel to stop using the current device and change to the second one that they were randomly assigned to use. They will continue to use the device and document the same information during weeks 5 and 6 of the study. Subjects who were seen in person will be instructed to return and see the PI or one of the study personnel after completing the activity and give the diaries and the devices to the PI or study personnel. Those subjects who are participating in the study virtually will be instructed to return and see the PI or one of the study personnel by zoom after completing the activity and return the diaries and the devices to the PI or study personnel by FEDEX, UPS or USPS. They will be asked questions about the use of the devices. During this in person or virtual visit, all participants will have the option to receive the commercially available wrist cooling device (valued at \$199), as compensation either in person or by FEDEX, UPS or USPS.

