In summary, there will be a total of two in-person visits for BUSM and local subjects and no in person visit for those are participating virtually 1.) During the first visit the subject will undergo consent process and randomization. Those subjects participating at BUSM or locally will receive the two devices and the diaries. Those subjects participating virtually will receive the two devices and diaries by FEDEX, UPS or USPS. They will be instructed how to use the diaries and the devices at the appropriate time. 2.) During the return visit at the end of the study the subject will be asked questions about the use of devices, and they will return the diaries and the devices either in person or by FEDEX, UPS or USPS. They will have the option to receive the commercially available cooling device as compensation for their participation in this study. There will be 3 telephone or zoom call visits including 1-3 days before the subject is scheduled/expected to use the assigned device during weeks 3 and 4 of the study and then a Zoom call our phone call 1-3 days before the subject is scheduled/expected to use the other device during weeks 5

Version number 1.8 and January 23, 2024

and 6 of the study. There may be multiple follow-ups calls if the subject is unable to start using the device on the indicated day. During week 6 before the end of the study they will get a reminder call to come back to return the diaries and the devices. The subjects in the virtual study will be reminded to send back the diaries and devices.

This is a double blinded crossover study; the devices will be in boxes that will be labeled as A or B. Only one co-investigator ([name]), who will not be communicating with the subjects will possess the information as to which one (A or B) of the labeled boxes that have a wrist cooling device that when turned on activates the fan and cooling porcelain plate or a wrist cooling device that when turned on only activates the fan. We will unblind the labels at the completion of the study for data analysis.

13 Assessment of Safety and Data Safety Monitoring Plan (DSMP)

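### Adverse effects are actively asked about only at the three calls, the last of which precedes the end of second-device use, and no record of onset date or device in use is described

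*Combined protocol and SAP*

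**What the plan says.** Section 13.2 gives two routes by which adverse effects reach the study team. The active one is that participants "at each telephone/zoom call will be asked if they have experienced any adverse effects". The passive one follows directly: "The subject will also have the opportunity to contact the study personnel or PI if they experience any adverse effects". No time limit is put on the second route.

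The calls are fixed elsewhere. The summary in section 12 states that "There will be 3 telephone or zoom call visits". Section 9.1.2 times them:

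- **Call 1:** "1-3 days before the expected date he/she will use the device during weeks 3 and 4 of the study".
- **Call 2:** "1-3 days before the expected date when the participant will use the other randomly assigned device during weeks 5 and 6". Section 12 also describes a contact at the end of week 4 telling the participant to stop the first device and change to the second.
- **Call 3:** "The subject will be contacted during week 6 of the study before the study end date", as a reminder to return devices and diaries.

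The schedule of events in the Appendix agrees, with call marks in weeks 2, 4 and 6.

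For the return visit, section 12 says of participants: "They will be asked questions about the use of the devices". The Appendix row for week 7 lists return of devices and diaries, the optional commercial device, and the same device-use questions. Section 16 describes the questionnaire on device use as the blinding assessment. The diaries, as described in sections 2, 4.2 and 12, hold hot flash severity and whether the device was used.

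**The concern.** Active questioning is tied to calls whose timing was set for another purpose, namely reminding participants to start, switch or return devices. As a result, no planned safety question clearly falls after device use has ended. Events late on the second device are picked up only if the participant volunteers them.

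The crossover adds an attribution problem. An event in the last days on the first device may first be asked about when the participant has been using the other device for a week or more. The protocol describes no field for when the event began or which device was in use, so it could be credited to the wrong device.

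This matters because section 6.2 says there are no prior clinical data supporting use of the device, and section 6.1 names impaired blood flow to the hand and discomfort as the risks. Section 13.4 sets no stopping rules. Section 13.3 has the investigator state at continuing review that the overall pattern of adverse events raises no new concern. That statement is only as good as the collection behind it. The primary analysis of hot flash severity is not affected.

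**Working it through.** The plan states no figure for safety coverage, so there is none to reproduce. The check places the calls on a day count.

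**Assumptions.** Day 1 is the first day of week 1 and the start is not delayed. The first device is used in weeks 3-4 (days 15-28) and the second in weeks 5-6 (days 29-42), 14 days each. A permitted delay in starting shifts all these dates together. The extra calls that section 12 allows for a delayed start come before device use and do not fill the gaps below.

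**Call 1**, 1-3 days before day 15: from 15 − 3 = day 12 to 15 − 1 = day 14. Device days already elapsed: 0. It can serve as a baseline but cannot yield device events.

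**Call 2**, 1-3 days before day 29: from 29 − 3 = day 26 to 29 − 1 = day 28.

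- Full first-device days after the call: 28 − 26 = 2 down to 28 − 28 = 0, that is 0-2 of 14 (0-14%).
- If the call is made at the very end of week 4, as section 12 has it, this is close to zero.

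**Call 3**, in week 6: days 36-42. Full second-device days after the call = 42 − call day.

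| Day of call 3 | Days left | Share of 14 |
|---|---|---|
| 36 | 6 | 43% |
| 39 | 3 | 21% |
| 41 | 1 | 7% |
| 42 | 0 | 0% |

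The range is 0-6 days. It is zero only if the call falls on the last day of device use.

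**Delay before late first-device events are asked about.** The interval from call 2 to call 3 runs from 36 − 28 = 8 days to 42 − 26 = 16 days. By call 3 the participant has completed between 36 − 29 = 7 and 42 − 29 = 13 days on the second device.

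**After the change proposed below.** With an adverse-effect question at the week-7 visit, second-device days after the last active enquiry fall from 0-6 to 0 for everyone who attends. The first-device interval is unchanged, but an onset date would assign the event to a device.

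**The case against.** The strongest reply is that the last days are not uncovered. Section 13.2 itself invites participants to contact staff about any adverse effect, with no end date, and the return visit is a conversation with study staff about the devices, where discomfort may well come up. This stands. A reader might infer that late events are never captured, or that the calls are the only safety data collection. The documents support neither. The gap is in active questioning. Nor do they say that the return visit is limited to device-use questions; they simply name no safety question there.

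Second, virtual participants have their return visit by zoom, and section 13.2 refers to each telephone or zoom call. Read literally, that visit could carry the safety question. Against this, section 12 counts the three calls apart from the return visit and the Appendix gives them separate rows. The point is ambiguous. If the zoom visit does count, virtual participants are asked after device use ends and in-person participants are not, which is a difference in ascertainment that also needs settling.

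Third, no adverse-event form or call script is reproduced, so the missing onset date and device field is a silence in the protocol and not proof that the forms lack them. Also fair. Misattribution is a possibility, reduced by fixed periods and by participants knowing which device they were using at the time.

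Finally, this is a 30-person pilot of a device treated as nonsignificant risk, with automatic shut-off and no safety endpoint. That limits the weight of the point, but a remedy this small is still worth making.

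**Conclusion.** The point holds as a gap in active ascertainment. Followed as written, the plan leaves the last 0-6 of 14 second-device days to spontaneous reports, unless the zoom return visit is treated as a call, and then only for virtual participants. The 43% is the upper end, reached only if the reminder call is made on the first day of week 6; it should not be read as the expected loss. On the first device, 0-2 full days fall after the second call, near zero under the end-of-week-4 wording. Events in that window are next asked about 8-16 days after the second call, with no described record of onset or device.

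These figures rest on the day count above and on the calls being made when scheduled. The documents do not show that any event would in fact be lost or credited to the wrong device. This is an inexpensive improvement to safety collection, with no bearing on the efficacy analysis.

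**What to change.** 1. In section 13.2 and in the week-7 row of the Appendix schedule, state that all participants, in person or virtual, will be asked at the return visit about any adverse effects since the last call. This also removes the ambiguity over the zoom return visit.
2. At every enquiry, record the onset date and whether the first or second device was in use. Recording the order rather than which device cools keeps the blind.
3. State that adverse events will be summarised by assigned device after unblinding.
4. Reconcile the two descriptions of the second contact (1-3 days before the switch in section 9.1.2 and the section 12 summary; end of week 4 elsewhere in section 12).

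The cost is one extra question at a visit that already takes place and two fields on a form. No call needs to move, no visit is added, and no clinical rule changes.
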